10.1.2 Recording and Reporting AEs

In this study, any AE occurring after the study participant has signed the informed consent form but *prior to* the initiation of study medication will be recorded as medical history. The commencement of AE collection will begin at the time of initiation of study medication (Cycle 1, Day 1). AE collection will continue up to and including the EOT visit. Those AEs that are determined to be related to the study treatment that are ongoing at the time of the EOT visit, will continue to be monitored until the event resolves or improves to baseline or Grade 1. For this study, the EOT visit may occur up to approximately 30 days after the last dose of study drug.

All AEs that occur during the defined study period must be recorded in the source documentation.

Signs and symptom will be recorded and entered into the database individually, except when considered manifestations of a medical condition or disease state. When such a diagnosis is made, all related signs, symptoms, and any test findings will be recorded collectively as a single diagnosis. A precise medical diagnosis will be recorded whenever possible.

Abnormal laboratory values or diagnostic test results will constitute AEs only if they induce clinical signs or symptoms or require treatment or further diagnostic tests. Disease progression will not be recorded as an AE.

When known, the onset and end dates, duration, action taken regarding study drug, and outcome for each AE should be recorded on the source documentation and entered in the study database. The guidelines relating to expectedness of each AE, relationship of each AE to study drug treatment and study procedures, and the severity and seriousness of each AE, as judged by the investigator, is described below.

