7.2.1 Procedures at Screening

A signed and dated informed consent form will be obtained before screening procedures commence. Evaluations obtained as part of routine medical care and performed during the screening period may be used for the protocol required evaluations.

After informed consent is obtained, participants who are screened will be assigned a unique identifier number such that all participants are given consecutive identification numbers in successive order.

A participant who is screened but not enrolled may be re-screened.

The following procedures and assessments will be performed within 28 days prior to C1D1 visit:

- Obtain histology report confirming diagnosis of malignancy
- Review inclusion/exclusion criteria
- Tumor evaluation through diagnostic imaging and RECIST v1.1 reading, including CT or MRI scans of chest, abdomen, and pelvis with contrast, and brain MRI, or PET CT scan
- Archival tumor samples will be collected for subjects for confirmation of diagnosis, as well as, for determination of exploratory mutational analysis.
- If no archival tumor samples are available, fresh biopsy will be collected for subjects for confirmation of diagnosis, as well as, for determination of exploratory mutational analysis.
- Review medical history (to include demographics, tobacco use (if smokes or smoked, and smoking pack year), surgical and psychiatric history and cancer treatment history)
- Review prior medication history (those medications taken within the last 28 days before the start of study treatment)
- Full physical examination including height, weight and vital signs measurements (temperature, heart rate, respiration rate and blood pressure).
- ECOG performance status
- Triplicate 12-lead ECG
- Clinical laboratory tests include hematology (complete blood counts with differential), serum chemistry (complete metabolic panel including Na, K, Cl, CO2, blood urea nitrogen, creatinine, glucose, aspartate aminotransferase, total bilirubin, alkaline phosphatase, alanine aminotransferase, albumin), coagulation profile including prothrombin time (PT), international normalized ratio (INR), partial thromboplastin time (PTT), CA 19-9, urinalysis)

The following procedures and assessments will be performed within 7 days prior to C1D1 visit:

Serum pregnancy test.

Participants who continue to meet all inclusion and exclusion criteria will be enrolled in the study.

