10.1 Adverse Events

10.1.1 Definition of an AE

An AE is any untoward medical occurrence in a participant administered a pharmaceutical product, regardless of whether it has a causal relationship with this treatment.

An AE can, therefore, be any unfavorable and unintended physical sign, symptom, or laboratory parameter that develops or worsens in severity during the course of the study, or significant worsening of the disease under study or of any concurrent disease, whether or not considered related to the study drug. A new condition or the worsening of a pre-existing condition will be considered an AE. Stable chronic conditions (such as arthritis) that are present before the participant signs the informed consent form and do not worsen during the study will not be considered AEs.

Accordingly, an AE can include any of the following:

- Intercurrent illnesses
- Physical injuries
- Events possibly related to concomitant medication
- Significant worsening (change in nature, severity, or frequency) of the disease under study or other pre-existing conditions. (Note: A condition recorded as pre-existing that is intermittently symptomatic [e.g., headache] and which occurs during the study should be recorded as an AE.)
- Drug interactions
- Events occurring during diagnostic procedures
- Laboratory or diagnostic test abnormalities that result in the withdrawal of the participant from the study, are associated with clinical signs and symptoms or an SAE, or require medical treatment or further diagnostic work-up, or are considered by the Principal Investigator to be clinically significant. Note: Abnormal laboratory test results at the screening visit that preclude a participant from entering the study or receiving study treatment are not considered AEs, but will be evaluated to monitor data from participants who do not meet screening criteria.
- All events of possible drug-induced liver injury with hyperbilirubinemia (defined as aspartate aminotransferase [AST] or alanine aminotransferase [ALT] ≥3 times the upper limit of the normal range [ULN], plus either bilirubin ≥2 times the ULN or international normalized ratio [INR]>1.5) or Hy's Law events require immediate study treatment cessation and reporting as a SAE.
- Disease progression (or progressive disease) or death due to disease progression will not be considered an AE or a SAE in this study, but will be collected as an efficacy assessment.

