10.3 Reporting of AEs and SAEs

10.3.1 Investigator Responsibility

An unanticipated AE is one that is deemed to be unexpected and related (reasonable possibility) to the investigational medication. All unanticipated AEs that occur during the protocol specific AE observation time period must be reported to the Principal Investigator immediately. If a serious unexpected AE is believed to be related to the study drug or study procedures, the Principal Investigator will take appropriate steps to notify all the appropriate regulatory authorities.

All SAEs will be reported to the sponsor within 24 hours of knowledge. SAEs will be reported to the sponsor using the MedWatch Form 3500A. Updates to the SAE should be made as events change.

The Sponsor-Investigator will submit a written IND Safety Report (i.e., completed FDA Form 3500A) to the responsible new drug review division of the FDA for any observed or volunteered adverse event that is determined to be a serious and unexpected, suspected adverse reaction. Each IND Safety Report will be prominently labeled, "IND Safety Report", and a copy will be provided to all participating investigators (if applicable) and sub-investigators.

Written IND Safety Reports will be submitted to the FDA as soon as possible and, in no event, later than 15 calendar days following the Sponsor-Investigator's receipt of the respective adverse event information and determination that it meets the respective criteria for reporting.

For each written IND Safety Report, the Sponsor-Investigator will identify all previously submitted IND Safety Reports that addressed a similar suspected adverse reaction experience and will provide an analysis of the significance of newly reported, suspected adverse reaction in light of the previous, similar report(s) or any other relevant information.

Relevant follow-up information to an IND Safety Report will be submitted to the applicable review division of the FDA as soon as the information is available and will be identified as such (i.e., "Follow-up IND Safety Report").

If the results of the Sponsor-Investigator's follow-up investigation show that an adverse event that was initially determined to not require a written IND Safety Report does, in fact, meet the requirements for reporting; the Sponsor-Investigator will submit a written IND Safety Report as soon as possible, but in no event later than 15 calendar days, after the determination was made.

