12.0 DATA HANDLING, DATA QUALITY ASSURANCE, AND RECORD KEEPING

12.1 Data Collection

Direct data entry into to the Penn State Cancer Institute OnCore CTMS will be utilized for this study. In addition to demographics, medical history, concomitant medications, and safety data, only those data needed to answer the study objectives will be included in the study database. The assessments and interventions noted in the *Protocol Required Interventions and Assessments* (Appendix B) will not be entered into the database. This data includes dates and results of physical examinations, vital signs, performance status, and laboratory results (CBC, Chemistry). Any abnormal results of the assessments will be captured as an AE according to the criteria noted in Section 10. Any concomitant medications administered for the purpose of procedures (anesthetics, etc.) will not be included in the data collection. AEs and SAEs will be recorded after the start of study drug until 30 days after discontinuation of study drug(s) or until a new anti-cancer treatment starts, whichever occurs first. AE that are ongoing at time will be checked or ongoing with no stop date. Unanticipated SAEs (ie. Serious, unexpected, and related (even remotely)) will be reported on the SAE Submission Form and entered in Oncore within 1 business day of discovery of the event. All other SAEs will be entered in the Oncore system within 5 business days. For screen failures (participants who sign the informed consent form but do not meet eligibility criteria), data relating to failure reason and demography will be captured.

Data will be reviewed for consistency by Data Management using both automated logical checks and manual review. The data collected will be reviewed and approved by the Principal Investigator or designated Co-investigator on an approximately quarterly basis depending on enrollment. Evidence of the Principal Investigator or Co-investigator review and approval may be done electronically in the OnCore CTMS. This approval acknowledges the Principal Investigator's review and acceptance of the data as being, to the best of his knowledge, complete, accurate, and current per the date documented on the form. Data will be verified using source documentation by the Study Monitor.

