${\bf APPENDIX~B-PROTOCOL~REQUIRED~INTERVENTIONS~AND~ASSESSMENTS}$

BASELINE ASSESSMENTS

| DAYS PRIOR TO C1D1 | ≤28 | ≤7 | COMMENTS |
|---------------------------------------------------------------------|-----|----|-----------------------------------------------------------------------------------------------------------------------------------------------------------------------------------------------------------------------------------------------------------------------------------------------------------------------------------------------------|
| Informed Consent | X | | |
| Assessment of eligibility | X | | |
| Enrollment path report | X | | |
| Diagnostic Imaging for Tumor Evaluation–RECIST v. 1.1 Reading | X | | Baseline CT or MRI scans of chest, abdomen, and pelvis with contrast, brain MRI or PET CT scans with contrast are performed if symptomatic. If hypersensitivity or known serious allergic reaction to CT contrast, consider MRI scans with gadolinium, or alternatively chest CT scans without contrast and abdomen/pelvic MRI scans with contrast. |
| Medical History | X | | including demographics, tobacco use (if smokes or smoked, and smoking pack year), surgical and psychiatric history and cancer treatment history |
| Physical Examination | X | | Height, weight and vital signs (temperature, heart rate, respiration rate, blood pressure). |
| Concomitant Medications | X | | |
| ECOG Performance Status | X | | |
| Triplicate 12-lead ECG | X | | Any ECG abnormalities at baseline will be followed up according to standard of care. |
| Hematology | X | | |
| Serum Chemistry | X | | Complete metabolic profile |
| Coagulation Profile | X | | |
| Urinalysis | X | | Basic and microscopic if abnormal sample is collected. |
| CA 19-9 | X | | |
| Archival Tumor Samples | X | | Formalin-fixed paraffin-embedded tumor is requested following confirmation of study eligibility. |
| Fresh Tumor Samples | X | | If archival tissue is unavailable or insufficient, repeat biopsy of tumor is as clinically indicated. |
| Pregnancy Test | | X | WOCP must have a negative serum pregnancy test between Day -7 to Day -1. |

Notes:

- Physical examination, including body weight
- Hematology: complete blood counts with differential

- Serum Chemistry: complete metabolic panel including Na, K, Cl, CO2, blood urea nitrogen, creatinine, glucose, aspartate aminotransferase, total bilirubin, alkaline phosphatase, alanine aminotransferase, albumin Coagulation Profile = PT,INR, PTT

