- Urinalysis In case of abnormal parameters microscopic evaluation should be performed.
- Tumor Samples (clinical routine) Archival or fresh tumor tissue is required for subjects with confirmation of diagnosis, as well as, for determination of exploratory mutational analysis as described in Section 1.3.4.
- Biomarker Blood Sample (extracellular vesicles (EV) isolation) will be collected at baseline (within 28 days prior to C1D1 visit) and every 8 weeks (at the onset of every 3rd cycle). Three lavender-top EDTA glass tubes will be used to collect approximately 5 ml of blood in each tube, and one 10-ml green-top sodium heparin tube will be used to collect approximately 7.5 ml of blood in the tube.

ON STUDY TREATMENT SCHEDULE OF ASSESSMENTS

| | Cycle | Cycle | Cycle 2 | Cycle 2 | Cycle 3-8 | |
|-----------------------------------------------------------------------|-------|--------------|---------|--------------|-----------|---------------------------------------------------------------------------------------------------------------------------------------------------------------------------------------------------------------------------------------------------------------------------------------------------------------------------|
| Day within Cycle | 1(+/- | 15(+/- 3) | 1(+/- | 15(+/ -3) | 1(+/- | Instructions |
| Physical Examination | X | X | X | X | X | Including vital signs (temperature, heart rate, respiration rate, blood pressure). |
| Weight | X | | X | | X | |
| ECOG Performance Status | X | X | X | X | X | |
| Adverse Events | X | X | X | X | X | CTCAE 5.0 |
| Concomitant Medication | X | X | X | X | X | |
| Diagnostic Imaging for Tumor Evaluation –RECIST v1.1 Reading | | | | | X | CT or MRI scans of chest, abdomen and pelvis with contrast are performed every other cycle (every 8 weeks ± 7 days). If hypersensitivity or known serious allergic reaction to CT contrast, consider MRI scans with gadolinium; alternatively chest CT scans without contrast and abdomen/pelvic MRI scans with contrast. |
| 12-lead ECG | X | | | | | ECG as a baseline and subsequently if clinically indicated. |
| Hematology | X | X | X | X | X | ≤ 3 days prior to day 1 of each cycle, unless more frequent assessment is clinically indicated. |
| Serum Chemistry | X | X | X | X | X | ≤ 3 days prior to day 1 of each cycle, unless more frequent assessment is clinically indicated. |
| CA 19-9 | X | | X | | X | |
| EORTC-QLQ-C30 | X | | X | | X | |

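### A serious, non-fatal complication of a screening biopsy before first dose need not be reported as an AE or SAE

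*Combined protocol and SAP*

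**What the plan says.** On the collection window, Section 10.1.2 provides that any AE arising after consent but before "the initiation of study medication will be recorded as medical history", and starts AE collection at Cycle 1 Day 1. Section 12.1 extends that start to serious events: "AEs and SAEs will be recorded after the start of study drug until 30 days after discontinuation of study drug(s". For screen failures, Section 12.1 captures only the reason for failure and demography. The safety analysis set (Section 8.2.2) is limited to participants with at least one dose.

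On what happens in the window, Sections 4.1 and 7.2.1 put screening after consent, and Section 7.2.1 places the main screening procedures in the 28 days before Cycle 1 Day 1. Among them: "If no archival tumor samples are available, fresh biopsy will be collected for subjects for confirmation of diagnosis". The same sentence adds exploratory mutational analysis as a purpose. Appendix B is less firm. Its baseline table says "If archival tissue is unavailable or insufficient, repeat biopsy of tumor is as clinically indicated", while the notes below it say "Archival or fresh tumor tissue is required for subjects with confirmation of diagnosis" and label the samples clinical routine.

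On procedure-related events, Section 10.1.1 lists "Events occurring during diagnostic procedures" among the things an AE can include. Section 10.1.2 expects each AE to be judged for its relationship to study procedures as well as to drug. Section 10.3.1 requires notice to the regulatory authorities on this condition: "If a serious unexpected AE is believed to be related to the study drug or study procedures".

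**The concern.** Starting all-cause AE collection at first dose is a common and defensible choice, because it keeps disease-related noise during screening out of the drug safety tables. The difficulty is that this rule has no exception for serious events or for events caused by the study's own procedures, and an invasive procedure can fall inside the excluded period. A participant admitted with a bleed or infection after a screening biopsy could be handled as having medical history, with no seriousness assessment, no attribution to the procedure and no clock for reporting. If the complication also prevents dosing, it may leave no AE record at all. That is the case the oversight bodies would most want to see.

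**Working it through.** No arithmetic applies and there is no figure in the plan to reproduce. The check sets the sections side by side.

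**Timeline.** Consent (Section 4.1), then screening within 28 days before Cycle 1 Day 1, including a fresh biopsy if no archival tissue exists (Section 7.2.1), then Cycle 1 Day 1, when AE and SAE recording starts (Sections 10.1.2 and 12.1). A screening biopsy, and any complication that begins before first dose, lies wholly before recording starts.

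**Routes for a serious, non-fatal, foreseeable complication before first dose:**

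| Route | Section | Start or condition | Catches it? |
|---|---|---|---|
| AE recording | 10.1.2 | Cycle 1 Day 1 | No; medical history |
| AE and SAE recording in the database | 12.1 | After study drug starts | No |
| Unanticipated AEs to the principal investigator | 10.3.1 | AE observation period | No |
| SAEs to the funder | 10.3.1 | Patients receiving study drug | No |
| SAEs to the sponsor in 24 hours | 10.3.1 | None stated | Unclear |
| SAEs to the DSMC in 10 working days | 10.2.1 table | None stated | Unclear |
| SAEs to the IRB | 10.3.1 | The IRB's own requirements | Unclear |
| Deaths to the DSMC in 24 hours | 10.2.1 table | Unless expected | Not if non-fatal |
| Unanticipated problems other than AEs or deviations, to the DSMC | 10.2.1 table | Must be unanticipated | Doubtful if foreseeable |
| Referral to the DSMC | 7.1.9 | Opinion of the investigator or monitoring team | Discretionary |
| Worsening of a pre-existing condition | 10.1.1 | After first dose | Only the later worsening |

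**The unclear rows.** Section 10.2.1 builds an SAE on an AE occurring at any dose, and Section 10.1.1 opens by defining an AE in a participant who has been given a product. Read with Sections 10.1.2 and 12.1, a site would most naturally conclude that a pre-dose event is not reportable. There is text pointing the other way. Section 10.1.1 excludes stable conditions by reference to consent, not first dose, and it specifically exempts screening laboratory results that preclude entry, which would be needless if nothing in screening could be an AE. The document therefore does not settle the matter, but its two explicit start rules both point to no reporting.

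**What record would remain.** For an enrolled participant, the event would sit in medical history and in the baseline summary (Section 8.3.2), outside the AE tables. For a screen failure, Section 12.1 would keep only the failure reason and demography.

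**Attribution.** Section 10.1.2 promises a judgement of relationship to study procedures, but the scale in Section 10.1.4 covers study drug only.

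**The case against.** The strongest case on the other side has four parts.

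First, the biopsy may not be a research procedure. Appendix B ties it to clinical indication and calls the samples clinical routine, the molecular profiling objective carries the same label, and confirmation of diagnosis is the first purpose named in Section 7.2.1. Every participant must already have histologic or cytologic evidence of disease (inclusion criterion 3), so many should have archival material. This stands in part. The sections disagree on how firmly the biopsy is required, and this write-up does not choose between them. Neither version removes the exploratory purpose stated in Section 7.2.1 and repeated in the Appendix B notes.

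Second, Sections 10.1.1 and 10.3.1 may simply concern procedures on treatment. A reader might infer that the screening biopsy is the only invasive procedure, so that the references to procedures can have no other meaning. The documents do not support that: Section 7.7.1 recommends an aspirate or biopsy of a residual lesion to confirm a complete response, which would fall after first dose. The tension with Section 10.1.2 is therefore not a flat contradiction.

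Third, a reader might infer that serious harm in screening cannot reach the DSMC or the IRB. That is too strong. Unexpected deaths, unanticipated problems and discretionary referral remain open, and the SAE rows state no start date. What remains is that a foreseeable, non-fatal complication need not be reported by any of them.

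Fourth, restricting the safety analysis set to dosed participants is a coherent choice for describing drug safety and is not itself a defect. That stands in full.

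**Conclusion.** The gap is real but narrow. As written, a serious, non-fatal complication of a screening biopsy that begins before first dose need not be recorded or reported as an AE or SAE, and if the participant becomes a screen failure it may leave no AE record.

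The size cannot be derived. The documents give neither the share of participants without archival tissue, nor a complication rate, nor an expected number of screen failures. All that can be said is that the number biopsied in screening lies between zero and everyone screened, against a planned enrollment of approximately up to 20. It would be tempting to attach an assumed percentage of biopsies, but such a figure would count biopsies, not harms, and has no basis in the plan.

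The conclusion rests on reading Sections 10.1.2 and 12.1 as governing the SAE rules that state no start date. It concerns participant safety oversight only and does not affect the ORR analysis. It is a cheap improvement, not a flaw that threatens the trial.

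**What to change.** Amend Sections 10.1.2 and 12.1 so that, from signed consent to first dose, all SAEs and any AE related to a study-mandated procedure are recorded and reported, including for participants who fail screening. Keep all-cause AE collection from Cycle 1 Day 1.

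Align Sections 10.2.1 and 10.3.1 with this by stating the start date for SAE reporting to the sponsor, DSMC and IRB, and adjust the opening definition in Section 10.1.1 so that it does not exclude a participant who has not yet been dosed. Add relationship to study procedures to the attribution scale in Section 10.1.4.

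Reconcile Section 7.2.1 with the Appendix B table and notes on the status of the fresh biopsy. Because all SAEs would be collected from consent, the serious-event part of the amendment works whichever way that is settled.

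In the analysis, list the pre-dose events separately and leave the safety analysis set as it is.

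The cost is a few sentences of amendment and a few extra records. The downside is that small addition to data collection during screening.
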